5.10 TEST DURATION

The trial will last 12 months after treating all the 24 included patients (12 in each trial arm).

6. TREATMENT AND STUDY PROCEDURES

6.1 IMP AND REFERENCE THERAPY

The product or drug under study is, in the control arm, the usual treatment based on of rehabilitation physiotherapy, postural hygiene and pharmacotherapy together with the injection of 2 ml 1% mepivacaine (obtained by mixing 1 ml of 2% mepivacaine with 1 ml of serum physiological saline) in the area of the paravertebral muscles close to the affected segment, using the same maneuvers as in the intervention in the experimental arm. (see section 2.4). In the experimental arm, the investigational drug or product is MSV, which are bone marrow mesenchymal cells processed according to the IBGM system from Valladolid, suspended in isotonic Ringer-lactate medium with human albumin at 0.5% and 5 mM glucose. Cell dose: $25x106 \pm 5x106$ MSV, in a volume of 2 ml of cell suspension. Stability demonstrated is> 12 hours at 4-20 °C. The whole process of obtaining MSV is carried out by highly qualified specialists in crops cell phones and is developed in the Cell Production Unit of Citospin (Parque Científico de

la UVa), meeting GMP criteria and following protocols approved by the AEMPS (PEI No. 10-134).

In the validations carried out, MSV has been shown to possess the characteristics typical MSC defined by the Society for Cellular Therapy (Dominici et al., 2006): 1) Adherence to plastic in cultivation; 2) Expression of CD73, CD90 and CD105 antigens. 3) Absence of hematopoietic antigens, markers of monocytes, macrophages and B lymphocytes.

4) In vitro differentiation capacity in osteoblasts, adipocytes and chondrocytes. Watch details in Figures 2 and 3.

6.1.1. Obtaining, cultivating and expanding MSV.

The processing and multiplication of harvested bone marrow cells using the IBGM procedure will last 3-4 weeks. The responsible medical team is expert in the management of the selection, culture and collection procedure of the cell product that, in its status available for application, is called MSV (the V added to the initials usual ones comes from Valladolid, to indicate that it follows the procedure developed, validated and authorized in our Cell Production Unit)).

As a cellular source for obtaining MSV, bone marrow aspirate is used from healthy donors submitted to the protocolized anticoagulant procedure. The protocol of obtaining is described in sections 5.3 and 6.1.6 and the consent documentation reported is included in Annex II. Once the bone marrow sample has been received (in a period less than 12 hours) and after checking the perfect condition of the shipment and the correct Completion of the accompanying documentation (informed consent of the donation, serologies, NAT etc), the bone marrow processing will be carried out in the Citospin facilities, in the Science Park of the University of Valladolid. In essence, the mononuclear cells are separated from the bone marrow aspirate by density gradient with Ficoll and subsequently a feasibility study is carried out mobile. During cultivation * 2 trypsinization processes or passes will be carried out, which have as an objective multiplying and purifying the cell line. In order to ensure that cells in culture are really MSV and the achievement of the established dose, the culture of will last for 3-4 weeks, until you have a sufficient number of cells (25x106 cells / intervened segment). The details of the specifications are those that appear in Production Guide (Preparation of Cell Therapy: expansion of mesenchymal cells bone marrow: FA-CMES-001-P). Serum samples will also be obtained from donor to carry out the mandatory serologies (RD 1301-2006, for cells and tissues human), performed using the PCR technique (NAT by Nucleic Acid Technology) to avoiding guarantine (Roth, 2010) and keeping a sufficient sample in the seroteca to further analysis, if necessary.

It has recently been conclusively shown that, contrary to what is stated in previous publications, there is no malignancy or genetic alterations in SCD maintained and expanded in vitro for prolonged periods (Bernardo et al., 2007; Bernardo et al., 2009; Bernardo et al., 2011), and that the initial errors were due to contamination with other immortalized cell lines grown in the same laboratory (de la Fuente et al., 2010; Torsvik et al., 2010; Vogel, 2010). At the end of the process, the characterization of the MSV will be carried out through studies immunophenotypic using flow cytometry, using the markers established for this type of cells, a higher positive cell phenotype should result (> 95%) for CD73, CD105, CD90, CD166 and negative (<10%) for CD45, CD14, CD34, CD31 and HLA-DR.

The cells will be packed in 5 ml syringes suspended in 2 ml of isotonic solution. Ringerlactate, supplemented with human albumin (0.5%) and glucose (5mM). The number of cells administered will be $25 \pm 5 \times 106$ cells. The sterility, cleanliness and quality control conditions of the production unit will be maintained following the steps defined in the Standard Procedures for Work established by the GMP norms of the "Cell Therapy Unit of the IBGM".

6.1.2. Conditioning and transport for shipment.

Once the MSVs are obtained, they will be resuspended in 2 ml of Ringer-lactate isotonic medium, supplemented with human albumin (0.5%) and glucose (5mM) to be

loaded into a 5 ml labeled syringe. This product has a stability of more than 12 hours at room temperature according to our protocol. The medicine will be transported in refrigerators validated for such activity, keeping it between 4 and 16 oC. It has been found that, in these conditions, it fully retains viability for> 12 hours (Orozco et al.,

2011).

6.1.3. Cell application.

Antibiotic prophylaxis will be performed with 2 g of IV cefazolin or 1 g of IV vancomycin in case allergy. The implantation of the cells is carried out under light sedation and radiological control. The cells are injected by puncture of the disc avoiding the neurovascular elements (Konings & Veldhuizen, 1988). After double brushing the region with a aqueous solution of povidone jodine (or chlorhexidine in patients allergic to iodine), The field is delimited with sterile sheets and local anesthesia (Scandicain 1%) is applied to the skin, subcutaneous tissue and muscle near the puncture. With fluoroscopy in position anteroposterior, a vertical line is marked on the skin corresponding to the projection of the spinous process with a sterile dermographic pencil. Then a line is drawn perpendicular corresponding to the projected image of an aligned Kirschner wire with the intervertebral space to be treated and a 20G spinal needle is inserted with an inclination 25 to 35 degrees toward the midline at a point 8 to 9 cm (depending on the patient morphotype) from the midline. At this time, fluoroscopy is switched to lateral position to ensure needle penetration follows the correct direction until the nucleus pulposus is reached. After verifying the correct position of the needle in the nucleus pulposus both in the anteroposterior fluoroscopic view and in the side, the cell suspension is slowly injected. Using this procedure, do not we had incidents in none of the 10 patients in our previous study (Orozco et al., 2011).

6.1.4 Post-treatment regime

The patient is discharged after a 2-hour observation period. Not prescribed Lumbostat corset and walking is allowed for moderate periods. Activity is suspended work for a week. Exercises to tone the muscles are prescribed para-vertebral and abdominal, which begin one month after the intervention. Medication analgesic is adapted to the needs of each patient and use should be avoided as far as possible of anti-inflammatories. Long-term follow-up will consist of clinical visits and monitoring Radiographic and MRI as specified in point 7.2 ("Schedule").

6.1.5. Possible complications derived from the proposed therapy.

The complications are the same as in the discography, and they occur very rarely. The most common complaint is exacerbation of pain for 1-2 weeks, which usually resolved by analgesia and muscle relaxants for a period short. The most serious complication is discitis, the incidence of which is less than 0.1% (Osti et al., 1990). Other complications described, although much less frequently, are transient headache, nausea, meningitis, epidural abscess, arachnoiditis, bruising intrathecal, retroperitoneal hematoma, cauda equina syndrome and acute disc herniation. Isolated cases of urticaria are not considered in this trial, as they are attributable to contrast medium. Initial fears about possible side effects of the Long-term discography regarding disc viability have not been confirmed. In a study with up to 20 years of clinical follow-up, no radiographic evidence was found of progressive disc degeneration after discography (Flanagan & Chung, 1986). The possible risk of complications derived from the use of allogeneic cells has been discussed in detail above. Suffice now to summarize that, according to the literature, the application of Allogeneic MSCs, both locally and systemically, have been shown to be safe both in the context of clinical trials and studies in animal models. Either way, will monitor skin and mucosal reactivity to watch for a possible immune reaction.

6.1.6. Methodology for obtaining bone marrow from donors.

This procedure will be applied to donors, generally included in the Eudra trial. CT2009-017405-11 (MSV_Artro) that we are carrying out or in compassionate cases authorized

by the AEMPS, and that follow the same protocol and that provide their cells left over for this test (see section 5.3).

The methodological protocol will be the one described in MSV Arto: Marrow punctureaspiration bone will be performed in the outpatient surgery operating room in a scheduled session. The patient in the prone position, accommodated with pillows, will undergo mild sedation. Then the surgical field will be brushed with alcoholic povidoneiodine solution (chlorhexidine if there is a history of allergy to iodine) and delimitation with sterile fields leaving both posterior iliac crests free. After local anesthesia (10 cc + 10 cc of 1% lidocaine, without vasoconstrictor) and sedation, two members of the extraction team, located at both sides of the operating table, with a 11 G trocar, various punctures located under the posterior superior iliac spine towards the joint sacroiliac (this is the area of the iliac with the highest trabecular density). The technique involves the Cortical perforation and sudden aspiration of a maximum of 1mL of bone marrow to avoid in peripheral blood aspiration is possible. The material obtained is injected into the bag supplied for transport that has previously been heparinized with an adequate dose to blood volume. The 2 successive aspirations are carried out by rotating 90° in the direction of the beveled trocar clockwise. The same puncture hole allows 1-2 depth mm about two times, repeating the same 1 mL aspiration methodology, change of syringe, 90° bevel rotation and new aspiration. The trocar can then be removed slightly and by sliding it a few millimeters over the cortex of the pelvis, the puncture, continuing on both sides of the pelvis until about 80 mL is achieved. immediately transport the marrow (sterile heparinized bag with a medium volume of 80 mL of aspirated bone marrow) to the Citospín Cell Therapy Unit, Parque UV scientist, under regulated conditions and room temperature (15 to 25 °C) in a maximum of 12 h.

6.2. TREATMENT ASSIGNMENT

6.2.1. Numerical correspondence of patients

The patients will be identified with a correlative number until the inclusion of the 24 patients (example: 001, 002, etc). In the event that an initially enrolled patient is need to be replaced, the assigned number would be the same one preceded by an R (example: R01, R02, etc).

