ANNEX VIII: MODIC CHANGES
ANNEX IX: RESEARCHER SIGNATURES PAGES A25
ANNEX X: INSURANCE POLICY
ANNEX XI: INSURANCE CERTIFICATE (Art.8; RD223 / 2004) A27

1. SUMMARY

Type of request:

Phase I-II, single-center, prospective, randomized, blinded ** and controlled clinical trial for the treatment of lumbar degenerative disc disease with allogeneic mesenchymal cells (MSV *), with two arms with 12 patients each. In the experimental arm, cells will be administered locally in the nucleus pulposus area of the affected segment "Ex Vivo" expanded allogeneic mesenchymal cells with the IBGM GMP procedure (MSV; PEI No. 10-134; authorized by the AEMPS). The control arm will infiltrate the area of the paravertebral musculature close to the injury with saline solution containing mepivacaine at 1% in the same volume and subject to the same maneuvers as the intervention on the arm experimental.

** Double blind, masked for the patient and evaluators performing the analysis of the results, open to the doctor who applies the cells.

Data relating to the Sponsor:

Citospin, Scientific Park of the University of Valladolid R + D Building, [name] NIF: NIF. B-47673538 Title of the clinical trial: Treatment of lumbar degenerative disc disease with allogeneic mesenchymal cells (MSV *). * MSV = Mesenchymal cells of the bone marrow prepared by the procedure of IBGM of Valladolid.

Protocol Code: Disc_allo_MSV Eudra-CT: 2012-004444-30

Experimental and control drug: dose, pharmaceutical form, route of administration, therapeutic group:

Experimental drug: The investigational drug or product is MSV, which is Mesenchymal bone marrow stromal cells obtained from healthy donors with negative serology (NAT; nucleic acid technology) and processed according to procedure of the IBGM (PEI Num. 10-134; approved by AEMPS), with the following characteristics: \Box Cell dose: 25x10e6 ± 5x10e6 MSV per disk.

□ Presentation: 2 ml of cell suspension in Ringer-lactate isotonic with 0.5% human albumin and 5 mM glucose in a 5 ml syringe. Stability:> 12 hours at 4-20 °C

□ Administration: Injection into the nucleus pulposus area of the affected disc

□ Therapeutic Group: Cell Therapy

Control drug: Injection of 2 ml of 1% mepivacaine in saline serum (see section 2.4). in the paravertebral musculature close to the injury, using the same volume and the same maneuvers as the intervention in the experimental arm.

Cell Production

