4.2 Overall study design

The study consists of 2 arms, one experimental with allogeneic MSV, and another control in the to be injected into the area of the paravertebral muscles near the injury saline serum containing 1% mepivacaine (1 ml of 2% mepivacaine + 1 ml of saline) in identical volume and subject to the same maneuvers as the intervention on the arm experimental. Participants in the study will be offered the possibility of, once completed the study, receive MSV treatment if it proves beneficial and the patient so wishes. The inclusion criteria in both arms are identical, but after recruiting patients will be randomly assigned to one of the treatments. The Cell manufacturing will be carried out by Citospin at the facilities of the Park Scientist of the UVa and the application and monitoring will be carried out at the Clinical Hospital University of Valladolid. 24 patients diagnosed with low back pain and / or low back pain attributable to disc degeneration and evidence of proven continuity of the external fibrous ring in the magnetic resonance image. The patients will be evaluated clinically, by the previous imaging studies (X-ray and MRI). If they are considered inclusive, they will be provided with the information regarding the clinical trial and the "Patient Information Sheet" (Annex II), citing them for the Inclusion visit. In the "Inclusion Visit", if the patient decides to participate in the trial, they must sign the "Informed Consent Document" and a visit will be scheduled for the practice of MRI and radiographs, which will be considered the pattern on which the possible determinable changes in the controls at 6 and 12 months. If you are MRI and X-rays have been recently performed and their characteristics are valid for the study, its repetition can be avoided. In this visit, basic analytics will also be requested, serology for HIV, lues and hepatitis B and C, and a serum sample will be obtained that will be sent to the Cell Production Unit for filing in the Seroteca. Although the Positive serology is not a criterion for exclusion of the recipient in the present test, it will be performed for epidemiological and preventive purposes. At the next visit (V0), it will be verified that all the inclusion criteria persist and that no exclusion is presented and the patient will be randomized (blind for him) in one of the two treatment groups and the date of implantation of MSV (V1). Once the mobile application is made, the patients will be followed up safety and to determine efficacy as established in the visit program (V2 to V5, see later).

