5.6 CRITERIA FOR WITHDRAWAL OF PATIENTS AND PROCEDURES TO FOLLOW

Patients can leave the study at any time, without having to give no explanation. Additionally, patients may be withdrawn from the study for the following reasons:

1. They have adverse events that affect participation in the study

2. They do not wish to continue (withdrawal of consent) for any reason.

3. Violation of protocol or significant deviation from specific procedures

of the study

4. Loss of follow-up

5. Appearance of a clinically significant intercurrent disease that affects the participation in the study.

6. The investigator considers that it is beneficial for the patient to withdraw from the study. The withdrawal of the patient from the study will not represent for him any type of damage in the control of their disease, in subsequent treatments or in the treatment to be received by the doctor. If a patient is withdrawn from the study at any time the reason must be recorded in the corresponding sheet of the data collection notebook (CRD). Patients who are withdrawn from the study due to an adverse event or abnormal results of laboratory values should be followed up to total trial resolution or for a period of time considered clinically reasonable by the researcher.

Patients withdrawn from the trial due to an adverse event will be included in security analysis. Patients who have undergone surgically intervened for graft insertion. If a patient is lost, an attempt should be made to contact him. The investigator it should reflect the loss of follow-up in the medical history.

The aim of the study is to obtain 12 evaluable patients in each trial arm (24 in total). A patient will be considered evaluable as long as it has been infiltrated into the space intervertebral a dose of MSV or belongs to the control group. In the event that for some cause the application cannot be made to an included patient, another must be included patient in the same group until reaching the 12 patients treated in each arm of the clinical trial. The study exit and the causes of the study exit of the initial patient and no further follow-up will be necessary since they will not have received the Trial treatment.

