10.3 DATA COLLECTION

10.3.1 Data collection notebook (CRD)

All the data generated in the clinical part of this study will be transcribed in the CRDs they will be printed in triplicate (carbonless paper). All data will be transcribed and modifications will be made in black ink. Any correction of the data must be signed, dated and with the reason for the modification noted. Only authorized personnel can enter data and make corrections in the CRD. The Investigator and study monitor will review all CRDs to ensure they are complete and legible and accurate. The monitor will instruct the center staff to make any necessary corrections or additions. The study monitor will have access to the medical records, original laboratory data and other related documents with the study, without compromising the identity of the patients. CRDs should be completed on a regular basis to keep data up to date and reflect the patient's condition in each period of the trial. The information collected and entered in the CRD will correspond to that of the source documents.

Patients will not be identified by name on the CRD, an ID will be used coded consisting of a patient number and initials. The researcher must carry out a confidential record (patient identification list) containing information about identification of the patient included in the trial in order to keep track of the themselves if necessary.

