11.3.1 Evaluable patients

A patient will be considered evaluable provided that he has undergone the specified interventions (Control or allogeneic MSV).

11.3.2 Efficacy population (Per protocol (PP) population):

Secondary efficacy endpoint analysis will be based on all patients who do not have incurred in major protocol violations, and have at least one rating final efficacy of the graft.

11.3.3 Safety population:

It is the population that includes all evaluable patients who have undergone one of the three study treatments. The security population will be the population of analysis of the safety variables of the treatment.

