11.5. DIFFICULTIES AND LIMITATIONS OF THE STUDY

As noted above, previous clinical trials show that a considerable improvement (up to 30%) due to the placebo effect. It will therefore be accurate discount this random effect before assessing the effects of MSVs. It is therefore, important evolution in the control group.

Bone marrow donation could be a problem if not enough were found donors. The solution to be used, when possible, by patients undergoing treatment with autologous mesenchymals (in the trial we are conducting in collaboration with CM Teknon) also as allogeneic donors would be the situation ideal, the most economical in terms of required means and the most interesting scientifically.

We have tried to obtain the maximum masking in the test within a design reasonable for this first study. While the "single blind" (patient) design is feasible without serious complications, the "double blind" (researcher) or "triple" (analysis) various logistical and ethical issues, so they have been left for the future. If there are indications of efficacy for allogeneic MSV, it will not be possible to perform direct comparison with autologous MSVs, so if these are obtained results, a new trial should be designed to directly compare the efficacy of both therapeutic alternatives.

REFERENCES:

Adams MA, Dolan P & Hutton WC. (1986). The stages of disc degeneration as revealed by discograms. The Journal of bone and joint surgery 68, 36-41. Adams MA, Freeman BJ, Morrison HP, Nelson IW & Dolan P. (2000). Mechanical initiation of intervertebral disc degeneration. Spine (Phila Pa 1976) 25, 1625-1636. Aggarwal S & Pittenger MF. (2005). Human mesenchymal stem cells modulate allogeneic immune cell responses. Blood 105, 1815-1822.

Bernardo ME, Locatelli F & Fibbe WE. (2009). Mesenchymal stromal cells. Ann N Y Acad Sci 1176, 101-117.

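### A replacement inherits the untreated patient's arm without a new concealed allocation, so staff who know that arm know the replacement's arm in advance; the R prefix may add a conditional hint to the MRI reader

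*Combined protocol and SAP*

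**What the plan says.** - **Allocation.** Section 4.2 places randomisation at V0, once the criteria have been rechecked and before treatment at V1: "the patient will be randomized (blind for him) in one of the two treatment groups". Section 6.2.2 has the CRO allocate centrally and at random, with the assignment held in a sealed envelope.
- **Replacement.** Section 5.6, in the replacement text (section 5.7 in the contents list), says that if the application cannot be made, "another must be included patient in the same group until reaching the 12 patients treated in each arm".
- **Numbering.** Section 6.2.1: "the assigned number would be the same one preceded by an R". Its examples are 001 for a first patient and R01 for a replacement.
- **Masking.** The summary and section 4.1 describe patient and evaluators as masked, and the trial as "open to the doctor who applies the cells".
- **Patient code.** On the data collection notebook (section 10.3.1), "an ID will be used coded consisting of a patient number and initials".
- **Evaluable patient.** Section 5.6 requires that the patient has had "infiltrated into the space intervertebral a dose of MSV or belongs to the control group". Section 11.3.1 instead applies one condition to both arms: the assigned intervention must have been carried out.
- **Supply.** Section 11.5 concedes: "Bone marrow donation could be a problem if not enough were found donors".

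**The concern.** Central random allocation with sealed envelopes protects the comparison only if nobody involved in enrolment can foresee the next assignment. The replacement rule is an exception to that protection. Once an allocated patient goes untreated, the next place is reserved for a known arm, and the person who fills it may not yet have been screened or have consented.

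Eligibility leaves room for judgement: exclusion criteria 4 and 11 (section 5.1.2) rest on the researchers' discretion or medical criteria. Foreknowledge combined with discretion can influence who is enrolled and when. Comparing the two arms is a stated secondary objective (section 3.2), and with 12 patients per arm a few non-randomised members form a visible share.

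A second, weaker issue is the label. If patients who cannot be treated come mainly from the MSV arm, an R on a notebook page or image would tell a masked reader something about the arm.

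**Working it through.** The plan's only figure here is the sample size: 12 + 12 = 24 (section 11.1). It is fixed without a power calculation and is not in dispute.

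**1. Is a replacement randomised?** Sections 4.2 and 6.2.2 describe one random draw per patient at V0. Section 5.6 assigns the replacement to its predecessor's group. Neither section 6.2.1 nor section 6.2.2 provides a new draw. The replacement's arm is therefore fixed before that person enters.

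**2. Who can know it?** The applying doctor is unmasked by design. The envelope still protects the replacement if the predecessor's was never opened, but the plan does not say when envelopes are opened. The footnote to the section 7.2 schedule requires cells to be obtained and expanded in the right time window, so whoever arranges an MSV dose would ordinarily learn the arm before V1. That last step is an inference.

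**3. Predictability.** Under the same-group rule it is 100% for a person who knows the predecessor's arm. Under a fresh simple 1:1 draw it is 50%. Under a fixed 12/12 list, after *a* MSV and *b* control patients have been treated, the chance that the next assignment is MSV is (12 − a)/(24 − a − b):
- a = 6, b = 6: 6/12 = 50%
- a = 10, b = 11: 2/3 = 67%
- a = 11, b = 12: 1/1 = 100%

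So 50% is a reference value, and late allocations are partly predictable in any case to someone keeping a tally.

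**4. Does the R point to MSV?** Let qs be the non-application rate common to both arms and qp the additional rate that exists only for MSV (donor or product failure). With equal arms:

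qC = qs; qM = 1 − (1 − qs)(1 − qp); P(MSV | R) = qM/(qM + qC).

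The documents give no rates, so every row below is an assumption.

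| qs | qp | qM | P(MSV given R) |
|---|---|---|---|
| 2% | 0% | 2.0% | 50% |
| 2% | 2% | 3.96% | 66% |
| 5% | 5% | 9.75% | 66% |
| 5% | 10% | 14.5% | 74% |
| 2% | 10% | 11.8% | 86% |
| 0% | any above 0 | qp | 100% |

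The last row is the case in which control patients are never replaced. It is the literal effect of the evaluable definition in section 5.6, which accepts controls by group membership alone. The next sentence there asks for 12 treated patients in each arm, and section 11.3.1 is symmetric, so the text does not settle the matter.

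**5. Which outcomes could the R reach?** Annexes V and VI show the pain scale and Oswestry index as completed by the patient, and the SF-12 is also a patient questionnaire. The R on the code does not tell the patient the arm. The T2 regions of interest (section 11.2.1.2) are placed by a reader. Section 10.3.1 puts the number on the notebook, but nothing states which code the MRI reader sees.

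**6. Share of an arm.** One replacement is 1/12 = 8.3% of an arm.

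**The case against.** The strongest case against has four parts.

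- **Foreknowledge needs links that the plan does not state.** It does not say that the applying doctor recruits or judges eligibility, nor when envelopes are opened. This stands as a limit on how certain any selection bias is. It does not restore concealment, because no provision keeps the predecessor's arm from those who enrol.
- **MSV-only failures need not produce replacements.** The product is allogeneic, section 5.3.3 foresees one to five additional batches from surplus cells, and section 5.3 gives an alternative donor source, so a failed batch might only delay treatment. Withdrawal of consent and intercurrent illness can occur in either arm. This stands. A reader might infer that R-coded patients will be mostly MSV, but without failure rates the documents allow anything from no information upwards.
- **Larger threats to masking exist.** Section 11.5 says masking beyond the patient was left for the future, which conflicts with the summary and section 4.1. The participation card in section 5.9 names the allogeneic cell treatment. This stands too: the R adds little to those.
- **The trial is primarily about feasibility and safety.** Section 3 calls the efficacy comparison preliminary. That lowers the stakes, but the comparison is still planned and the correction is cheap.

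The R01 example also leaves unclear whether R numbers link to the predecessor or form a new series. The same-group rule holds under either reading.

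**Conclusion.** The concealment point holds. A replacement bypasses the random sealed-envelope allocation, and its arm is certain in advance to anyone who knows the predecessor's arm, at least the unmasked applying doctor. It fails only where the predecessor's envelope stayed closed, which the plan does not require.

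The masking point holds conditionally. The R may hint at MSV to the reader of the T2 regions of interest if non-application is more frequent in the MSV arm and if that reader sees the patient number. The assumed rates above give 50% to 86%, and 100% only if controls are never replaced.

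A reader might go further and conclude that pain and disability scores of R-coded patients are unmasked, or put a number of VAS points on the bias. The documents support neither: those scores come from the patient, and no replacement rate or bias size is given or derivable. The size that can be stated is 1/12 (8%) of an arm per replacement. This is a worthwhile correction to a stated rule, and it does not show that the results would be biased.

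**What to change.** Amend section 6.2.1 and the replacement text of section 5.6:

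1. When an allocated patient is not treated, the CRO returns that assignment to the remaining unopened ones and re-permutes them.
2. The next eligible, consented patient receives the next consecutive number (025, 026 and so on as needed) and the next concealed assignment.
3. Drop the R prefix from notebooks, images and questionnaires, and keep the link to the replaced patient only in the CRO file.
4. Reconcile the definitions of an evaluable patient in sections 5.6 and 11.3.1, so that the condition for replacement is the same in both arms.

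This keeps 12 treated patients per arm. A simple fresh 1:1 draw would also remove certainty about the arm but could leave unequal arms. The standard-error ratio √[(1/a + 1/b)/(1/12 + 1/12)], with a and b here the two arm sizes, is 1.004 for 11/13 and 1.014 for 10/14, a small loss that re-permuting avoids.

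The cost is a wording change and one CRO step per replacement, including reissue of any envelopes held at the site. One weakness remains: at the very end of the list the arm is still predictable, as the last case in step 3 of the working shows.
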